13 APPENDIX A: PERFORMANCE STATUS CRITERIA

ECOG Performance Status Scale		Karnofsky Performance Scale	
Grade	Descriptions	Percent	Descriptions
0	Normal activity. Fully active, able to carry on all pre-disease performance without restriction.	100	Normal, no complaints, no evidence of disease.
		90	Able to carry on normal activity; minor signs or symptoms of disease.
1	Symptoms, but ambulatory. Restricted in physically strenuous activity, but ambulatory and able to carry out light or sedentary work (e.g., light housework, office work).	80	Normal activity with effort; some signs or symptoms of disease.
		70	Cares for self, unable to carry on normal activity or to do active work.
2	In bed < 50% of the time. Ambulatory and capable of all self-care, but unable to carry out any work activities. Up and about > 50% of waking hours.	60	Requires occasional assistance, but is able to care for most of his/her needs.
		50	Requires considerable assistance and frequent medical care.
3	In bed > 50% of the time. Capable of only limited self-care, confined to bed or chair > 50% of waking hours.	40	Disabled, requires special care and assistance.
		30	Severely disabled, hospitalization indicated. Death not imminent.
4	100% bedridden. Completely disabled. Cannot carry on any self-care. Totally confined to bed or chair.	20	Very sick, hospitalization indicated. Death not imminent.
		10	Moribund, fatal processes progressing rapidly.
5	Dead.	0	Dead.

15 APPENDIX C : FOLLOW-UP EVALUATIONS

STUDY CALENDAR

Surveillance ARM – PROSTVAC: surveillance for 6 months followed by vaccinia-PROSTVAC, 2×10^8 infectious units subcutaneously in week 1 and fowlpox-vaccine 1×10^9 infectious units subcutaneously given in week 3, week 5 and then monthly for a total of 6 months of treatment. After this 6-month treatment period is complete, patients will then have the option of fowlpox-vaccine 1×10^9 q 3 months for 1 year while in follow-up.

	Screening/ Baseline ¹¹	Surveillance for 6 months							1 cycle = 28 days; C=Cycle; D=Day											
		M -6	M -5	M-4	M-3	M-2	M-1	C1 D1	C1 D15	C2 D1	C3 D1	C4 D1	C5 D1	C6 D1	C7 D1	C8 D1	C9+ D1 ^{6,7}	End of study		
Informed Consent / Registration	X																			
Randomization	X																			
TREATMENT																				
rV-PROSTVAC									X											
rF-PROSTVAC										X	X	X	X	X	X		X ⁹			
EVALUATION																				
History and PE, Height and Weight	X		X		X		X		X	X	X	X	X	X	X	X	X ¹	X		
ECOG Performance Score	X																			
Pathologic confirmation of dx	X ²																			
Laboratory Testing																				
CBC with differential	X								X	X	X	X	X	X	X	X	X ¹	X		
Serum chemistries (Na ⁺ , K ⁺ , Cl ⁻ , CO ₂ , glucose, BUN, creatinine, albumin, calcium, alkaline phosphatase, ALT, AST, total bilirubin, LDH,)	X								X	X	X	X	X	X	X	X	X ¹	X		
CK, uric acid, total protein, magnesium, phosphorus,	X																			

	Screening/ Baseline ¹¹	Surveillance for 6 months							1 cycle = 28 days; C=Cycle; D=Day											
		M -6	M -5	M-4	M-3	M-2	M-1	C1 D1	C1 D15	C2 D1	C3 D1	C4 D1	C5 D1	C6 D1	C7 D1	C8 D1	C9+ D1 ^{6,7}	End of study		
Urinalysis	X																			
Serum PSA and Testosterone	X	X	X	X	X	X	X	X	X	X	X	X	X	X	X	X ¹	X			
Hep B/HepC, HIV	X ³																			
Lymphocyte Phenotyping (CD4/CD8) ¹²	X							X	X	X	X	X	X	X	X	X ¹	X			
PAP (prostatic acid phosphatase)	X							X	X	X	X	X	X	X	X	X	X			
ECG	X ⁵																			
Tc 99 scintigraphy	X ⁴							X								X ⁶				
CT-C/A/P, or MRI	X ⁴							X								X ⁶				
Research Bloods	X							X		X				X		X ⁷	X ⁸			
FACT- P survey ¹⁰		X ¹⁰						X ¹⁰			X ¹⁰			X ¹⁰			X ¹⁰			
MSK Anxiety Survey ¹⁰		X ¹⁰						X ¹⁰			X ¹⁰			X ¹⁰			X ¹⁰			
Adverse Events	X		X		X		X	X									→			
Concomitant Medications	X							X									→			

Footnotes:

¹ HPE, CBC, Chem, PSA, and Lymphocyte Phenotyping will be obtained every cycle. For week 3 and week 5, these tests can be done +/- 3 days and for cycle 3 to cycle 6, they can be done +/- 14 days for logistical reasons. Vaccine can be given +/- 3 days for week 3 and week 5 and for cycle 3 to cycle 6, it can be given +/- 14 days for logistical reasons. Research blood will be drawn +/- 3 days for C1D1, C2D1 and +/- 14 days for C6D1 and C9D1 for logistical reasons.

² Pathologic confirmation will be obtained any time prior to enrollment

³ HepB/HepC/HIV status will be obtained within 8 weeks prior to enrollment

⁴ Screening Tc99 scintigraphy and CT-CAP or MRI will be obtained within 8 weeks prior to enrollment

⁵ Baseline ECG will be obtained within 8 weeks prior to enrollment

⁶ Restaging will be done every 6 months (+/- 14 days) or earlier if clinically indicated. If, however, in the opinion of the investigator re-staging scans are not required (in patients with a PSA DT > 6 months over the previous 6 months) then re-staging scans can be deferred, document in chart to assure compliance. However, once PSA DT is less than 6 months, scans must be performed.) Re-staging scans may exclude CT Chest.

⁷ Patients will continue to be followed after Cycle 9 until progression or ADT is clinically indicated. All visits will include evaluations listed for cycle 9 except research blood. Research blood will not be drawn after Cycle 9.

⁸optional

⁹Patients will have the option to initiate 1 year of vaccine maintenance within 3 months of cycle 6 vaccine, administered every 12 weeks. This year will include follow-up every 6 weeks during this period for PSA checks on non-vaccine visits. (Patients seen every 6 weeks during 1 year maintenance period). Patients will be required to have a PSADT greater than 5 months, as measured over the prior 6 months in order to start and continue vaccine during the 1 year maintenance period.

¹⁰Surveys are optional at all time points and can be done every 3 months for the first 9 months and every 3-4 months thereafter while patients are on-study. (If surveys are not done, reason will be documented.)

¹¹ Refer to sections **2.2** for screening evaluation and **2.4** for baseline evaluation

¹² Not performed at DFCI site.

-All patient visits can be delayed by 2 weeks for logistical issues except for week 3 and 5 where the window is 3 days.

Immediate Vaccine ARM– PROSTVAC (vaccinia-PROSTVAC, 2×10^8 infectious units subcutaneously in week 1 and fowlpox-vaccine 1×10^9 infectious units subcutaneously given in week 3, and week 5, then monthly for a total of 6 months of treatment. After this 6-month treatment period is complete, patients will then have the option of fowlpox-vaccine 1×10^9 q 3 months for 1 year))

	Screening/ Baseline ¹¹	Treatment	1 cycle = 28 days; C=Cycle; D=Day										
		C1 D1	C1 D15	C2 D1	C3 D1	C4 D1	C5 D1	C6 D1	C7 D1	C8 D1	C9+ D1 ^{6,7}	End of study	
Informed Consent / Registration	X												
Randomization	X												
TREATMENT													
rV-PROSTVAC			X										
rF-PROSTVAC				X	X	X	X	X			X ⁹		
EVALUATION													
History and PE, Height and Weight	X			X	X	X	X	X	X	X	X ¹	X	
ECOG Performance Score	X												
Pathologic confirmation of dx	X ²												
Laboratory Testing													
CBC with differential	X			X	X	X	X	X	X	X	X ¹	X	
Serum chemistries (Na ⁺ , K ⁺ , Cl ⁻ , CO ₂ , glucose, BUN, creatinine, albumin, calcium, magnesium, phosphorus, alkaline phosphatase, ALT, AST, total bilirubin, LDH.	X			X	X	X	X	X	X	X	X ¹	X	
CK, uric acid, total protein, magnesium, phosphorus,	X												
Urinalysis	X												
Serum PSA and Testosterone	X	X	X	X	X	X	X	X	X	X	X ¹	X	
Hep B/HepC, HIV	X ³												

	Screening/ Baseline ¹¹	Treatment	1 cycle = 28 days; C=Cycle; D=Day										
		C1 D1	C1 D15	C2 D1	C3 D1	C4 D1	C5 D1	C6 D1	C7 D1	C8 D1	C9+ D1 ^{6,7}	End of study	
Lymphocyte Phenotyping (CD4/CD8) ¹²	X			X	X	X	X	X	X	X	X ¹	X	
PAP (prostatic acid phosphatase)	X	X	X	X	X	X	X	X	X	X	X	X	
Research bloods	X			X				X			X ⁷	X ⁸	
ECG	X ⁵												
FACT- P survey ¹⁰		X ¹⁰			X ¹⁰			X ¹⁰			X ¹⁰		
MSK Anxiety Survey ¹⁰		X ¹⁰			X ¹⁰			X ¹⁰			X ¹⁰		
Tc 99 scintigraphy	X ⁴									X ⁶			
CT-C/A/P, or MRI	X ⁴									X ⁶			
Adverse Events	X	—						►					
Concomitant Medications	X	—						►					

Footnotes:

¹HPE, CBC, Chem, PSA, and Lymphocyte Phenotyping will be obtained every cycle including maintenance vaccine dosing. For week 3 and week 5, these tests can be done +/- 3 days and for cycle 3 to cycle 6, they can be done +/- 14 days for logistical reasons. Vaccine can be given +/- 3 days for week 3 and week 5 and for cycle 3 to cycle 6, it can be given +/- 14 days for logistical reasons. Screening labs within 16 days can be used for C1D1 serum PSA, testosterone, and PAP. Research blood will be drawn +/- 3 days for C2D1 and +/- 14 days for C6D1 and C9D1 days for logistical reasons.

² Pathologic confirmation will be obtained anytime prior to enrollment

³ HepB/HepC/HIV status will be obtained within 8 weeks prior to enrollment

⁴ Screening Tc99 scintigraphy and CT-CAP or MRI will be obtained within 8 weeks prior to enrollment

⁵ Baseline ECG will be obtained within 8 weeks prior to enrollment

⁶ Restaging will be done every 6 months (+/- 14 days) or earlier if clinically indicated. If, however, in the opinion of the investigator re-staging scans are not required (in patients with a PSA DT > 6 month over the previous 6 months, document in chart to assure compliance) then re-staging scans can be deferred. However, once PSA DT is less than 6 months, scans must be performed.) Re-staging scans may exclude CT Chest.

⁷ Patients will continue to be followed after Cycle 9 until progression or ADT is clinically indicated. All visits will include evaluations listed for cycle 9 except research blood. Research blood will not be drawn after Cycle 9..

⁸optional

⁹ Patients will have the option to initiate 1 year of vaccine maintenance within 3 months of cycle 6 vaccine, administered every 12 weeks. This year will include follow-up every 6 weeks during this period for PSA checks on non-vaccine visits. (Patients seen every 6 weeks during 1 year maintenance period). Patients will be required to have a PSADT greater than 5 months, as measured over the prior 6 months in order to start and continue vaccine during the 1 year maintenance period.

¹⁰Surveys are optional at all time points and can be done every 3 months for the first 9 months and every 3-4 months thereafter while patients are on-study. (If surveys are not done, reason will be documented.)

¹¹ Refer to sections [2.2](#) for screening evaluation and [2.4](#) for baseline evaluation

¹² Not performed at DFCI site.

-All patient visits can be delayed by 2 weeks for logistical issues except for week 3 and 5 where the window is 3 days.

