2 ELIGIBILITY ASSESSMENT AND ENROLLMENT

2.1 ELIGIBILITY CRITERIA

2.1.1 Inclusion Criteria

2.1.1.1 Histopathological documentation of prostate cancer confirmed in either the Laboratory of Pathology at the National Institutes of Health (NIH) Clinical Center, Walter Reed National Military Medical Center, MSKCC, DFCI or BIDMC prior to enrollment. If no pathologic specimen is available, patients may enroll with a pathologist's report showing a histologic diagnosis of prostate cancer and a clinical course consistent with the disease.

2.1.1.2 Biochemical progression after definitive radiation or surgery defined as follows:

- For patients following definitive radiation therapy: a rise in PSA of ≥ 2 ng/mL above the nadir (per RTOG-ASTRO consensus criteria).
- For patients following radical prostatectomy: rising PSA after surgical procedure. (Patients must have a PSA ≥ 0.8 ng/ml)

2.1.1.3 ECOG performance status of 0–1 (Karnofsky $\geq 80\%$, see **APPENDIX A**).

2.1.1.4 Patients must have a PSA doubling time of 5–15 months.

2.1.1.5 Patients must have a rising PSA as confirmed by 3 values done at least 1 week apart and over no less than 1 month.

- 2.1.1.6 Recovery from acute toxicity related to prior therapy, including surgery and radiation, or no toxicity \geq grade 2.
- 2.1.1.7 Negative CT scan/MRI and bone scan for metastatic prostate cancer.
- 2.1.1.8 Hematological eligibility parameters (within 16 days before starting therapy; see **APPENDIX D**):
 - Granulocyte count $\geq 1000/\text{mm}^3$
 - Platelet count $\geq 100\,000/\text{mm}^3$
 - Hgb $\geq 10\text{ g/dL}$
- 2.1.1.9 Biochemical eligibility parameters (within 16 days before starting therapy):
 - Hepatic function: bilirubin $\leq 1.5\text{ mg/dL}$ (OR in patients with Gilbert's syndrome, a total bilirubin ≤ 3.0), AST and ALT ≤ 2.5 times upper limit of normal.
- 2.1.1.10 No other active malignancies within the past 36 months (with the exception of nonmelanoma skin cancers or carcinoma in situ of the bladder) or life-threatening illnesses, in the opinion of the investigator.
- 2.1.1.11 Willing to travel to the NIH, MSKCC, DFCI, BIDMC for follow-up visits.
- 2.1.1.12 18 years of age or older.
- 2.1.1.13 Able to understand and sign informed consent.
- 2.1.1.14 Baseline testosterone $\geq 100\text{ ng/dl}$
- 2.1.1.15 PSA $\leq 30\text{ ng/mL}$.

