2.1.2 Exclusion Criteria

- 2.1.2.1 Immunocompromised status due to:

- Human immunodeficiency virus (HIV) positivity.
- Active autoimmune diseases such as Addison's disease, Hashimoto's thyroiditis, systemic lupus erythematosus, Sjogren syndrome, scleroderma, myasthenia gravis, Goodpasture syndrome or active Grave's disease. Patients with a history of autoimmunity that has not required systemic immunosuppressive therapy or does not threaten vital organ function including CNS, heart, lungs, kidneys, skin, and GI tract will be allowed.
- Other immunodeficiency diseases
- Splenectomy

- 2.1.2.2 Chronic administration (defined as daily or every other day for continued use > 14 days) of corticosteroids deemed systemic by investigator within 28 days before the first planned dose of PROSTVAC. Use of inhaled steroids, nasal sprays, intra-articular injections and topical creams for small body areas is allowed.
- 2.1.2.3 Serious intercurrent medical illness that, in the judgment of the investigator, would interfere with patient's ability to carry out the treatment program.
- 2.1.2.4 Other medications used for urinary symptoms including 5-alpha reductase inhibitors (finasteride and dutasteride) and alternative medications known to alter PSA (eg phytoestrogens and saw palmetto)
- 2.1.2.5 History of prior chemotherapy
- 2.1.2.6 History of prior immunotherapy within the last 3 years
- 2.1.2.7 Major surgery within 4 weeks prior to enrollment (Day 1 visit).
- 2.1.2.8 History of allergic reactions attributed to compounds of similar chemical or biologic composition to poxviral vaccines (e.g., vaccinia vaccine)
- 2.1.2.9 Known allergy to eggs, egg products, aminoglycoside antibiotics (for example, gentamicin or tobramycin).
- 2.1.2.10 History of atopic dermatitis or active skin condition (acute, chronic, exfoliative) that disrupts the epidermis
- 2.1.2.11 Previous serious adverse reactions to smallpox vaccination
- 2.1.2.12 Unable to avoid close contact or household contact with the following high-risk individuals for three weeks after the Day 1 vaccination: (a) children \leq 3 years of age, (b) pregnant or nursing women, (c) individuals with prior or concurrent extensive eczema or other eczemoid skin disorders, or (d) immunocompromised individuals, such as those with HIV.
- 2.1.2.13 Receipt of an investigational agent within 28 days (or 56 days for an antibody-based therapy) before the first planned dose of study drugs.
- 2.1.2.14 Patients who test positive for HBV or HCV

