2.2 SCREENING EVALUATION

- A. Pathological confirmation of diagnosis by either the Laboratory of Pathology at the NIH, Walter Reed National Military Medical Center, MSKCC, DFCI, or BIDMC may

be obtained anytime prior to enrollment (if specimen is available). If no pathologic specimen is available, patients may enroll with a pathologist's report showing a histologic diagnosis of prostate cancer and a clinical course consistent with the disease.

- B. The following parameters will be obtained within 8 weeks prior to enrollment:
 - 1. HIV test
 - 2. Hepatitis B and C
 - 3. Tc-99 whole-body scintigraphy
 - CT (or MRI may be substituted at investigator's discretion) of chest, abdomen and pelvis
- C. The following parameters will be obtained within 16 days prior to enrollment (cycle 1 day 1 for immediate treatment arm [Arm A], or M-6 visit for surveillance first arm [Arm B]):
 - 4. History and physical examination with ECOG
 - 5. Serum PSA
 - 6. Complete blood count plus differential and platelet count
 - 7. Hepatic and Acute Care
 - 8. Testosterone level

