2.4 BASELINE EVALUATION

- A. The following parameters will be obtained **within 8 weeks** prior to treatment initiation:
 1. Baseline electrocardiogram (EKG) on all patients, and appropriate cardiologic evaluation, as clinically indicated, to provide baseline function and identify any patients who should be monitored closely for cardiac risks associated with vaccinia vaccination.
- B. The following parameters will be obtained **within 16 days** prior to start of treatment (these tests will not need to be repeated if they were done at screening within the appropriate timeframe):
 1. Clinical evaluation
 - History and physical examination
 - ECOG performance status (see **APPENDIX A**)
 - Height, weight

2. Laboratory studies

- Serum PSA
CBC/differential, with platelet count
- Serum testosterone level
- Serum chemistries (Na⁺, K⁺, Cl⁻, CO₂, glucose, BUN, creatinine, albumin, calcium, magnesium, phosphorus, alkaline phosphatase, ALT, AST, total bilirubin, LDH, CK, uric acid, total protein)
- Lymphocyte phenotyping CD3/CD4/CD8
- Urinalysis in patients unless no feasible (i.e. patient has incontinence)
- PAP (prostatic acid phosphatase), at the discretion of the PI

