3.5.3 Laboratory Studies

(See also APPENDIX C)

- Serum PSA
- CBC/differential with platelet count
- Serum testosterone level
- Serum chemistries (Na⁺, K⁺, Cl⁻, CO₂, glucose, BUN, creatinine, albumin, calcium, magnesium, phosphorus, alkaline phosphatase, ALT, AST, total bilirubin, LDH, CK, uric acid, total protein)
- HIV/Hepatitis B/Hepatitis C tests (within 8 weeks prior to start of enrollment)
- Lymphocyte phenotyping CD3/CD4/CD8

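### In Arm B the HIV, HBV and HCV results are at least 168 days old at the first live vaccinia dose, against at most 56 days in Arm A, and no repeat test is scheduled

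*Combined protocol and SAP*

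**What the plan says.** All references are to the combined protocol and SAP.

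- **Serology is dated to enrolment wherever a window is given.** Section 2.2 B sets an 8-week window before enrolment. Section 3.5.3 lists "HIV/Hepatitis B/Hepatitis C tests (within 8 weeks prior to start of enrollment". Footnote 3 of both Appendix C calendars says "HepB/HepC/HIV status will be obtained within 8 weeks prior to enrollment".
- **Enrolment differs by arm.** Section 2.2 C writes "enrollment (cycle 1 day 1 for immediate treatment arm [Arm A], or M-6 visit for surveillance first arm [Arm B". In Arm A that is the day of the first vaccinia dose. The Arm B calendar describes "surveillance for 6 months followed by vaccinia-PROSTVAC", so in Arm B enrolment comes six months before the dose.
- **The pre-treatment baseline omits serology.** Section 2.4 B is dated "prior to start of treatment (these tests will not need to be repeated if they were done at screening within the appropriate timeframe". It lists history, physical examination, blood count, chemistries, lymphocyte phenotyping and other items, but not HIV, HBV or HCV. The serology row of the Arm B calendar has a single mark, under screening.
- **No maximum age is set.** Section 4.1.1 requires the HIV result before treatment without saying how recent it must be. It also allows immunologic studies to be repeated more often if clinically indicated.
- **The ECG is dated in two ways.** Section 2.4 A requires it within 8 weeks before treatment starts. Arm B footnote 5 places it within 8 weeks before enrolment.

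**The concern.** HIV, HBV and HCV positivity are exclusions because of what the vaccine might do to a man with impaired immunity, so the date that matters clinically is the date of the dose. Section 11.2 describes the vaccinia component as able to replicate in mammalian cells, with systemic infection possible.

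For HIV the rationale is direct. Section 10.1.3 cites the higher risk of serious effects from infectious vaccines. Section 11.2.6 bars the vaccinia product in immunocompromised men, including those with HIV infection, and lists HIV among the settings in which progressive vaccinia, with its high mortality, has been seen. For hepatitis, section 10.1.3 gives only possible immune impairment.

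A man in Arm B who acquires an infection, or whose infection becomes detectable, after the entry test could receive live vaccinia with nothing in the schedule that would find it. The two arms are thus screened to different standards for the same product. This is a patient-safety point. It does not bear on sample size, power or the month 0 to 6 primary comparison.

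**Working it through.** The plan states no age for the serology result at first dose, so there is no figure to reproduce. The check is date arithmetic.

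**Inputs**

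- Serology window: 8 × 7 = 56 days before enrolment (2.2 B, 3.5.3, footnote 3).
- Enrolment to first vaccinia: 0 days in Arm A; six months in Arm B (2.2 C, Appendix C).
- Six months in days: the plan does not define a surveillance month. Appendix C gives 28 days for a treatment cycle only. Two conventions are shown as assumptions: 6 × 28 = 168 days, or six calendar months, which run from 181 to 184 days depending on the start date.
- Visit delay: Appendix C lets visits other than weeks 3 and 5 slip by two weeks, 14 days.

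**Formula**

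Age at first vaccinia = (0 to 56 days before enrolment) + (enrolment to C1D1) + (0 or 14 days' delay).

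| | Tested on enrolment day, no delay | Tested 56 days before, no delay | Tested 56 days before, one 14-day delay |
|---|---|---|---|
| Arm A (enrolment is C1D1) | 0 | 56 | not applicable |
| Arm B, 28-day months | 168 | 168 + 56 = 224 | 224 + 14 = 238 |
| Arm B, calendar months | 181 | 184 + 56 = 240 | 240 + 14 = 254 |

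The lowest Arm B value is 168/56 = 3.0 times the highest Arm A value.

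**Sensitivity to the meaning of enrolment.** If enrolment meant registration and C1D1 in Arm A then slipped by 14 days, the Arm A maximum would be 56 + 14 = 70 days. The Arm B gap would not shorten.

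**ECG windows.** Counting back from C1D1 with 28-day months and no delay, section 2.4 A allows days 56 to 0 before the dose, and footnote 5 allows days 224 to 168. The windows are 168 − 56 = 112 days apart (181 − 56 = 125 at the least with calendar months), so one ECG cannot meet both.

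**Would a repeat at M-1 fit?** M-1 is 28 days before C1D1, or 28 to 31 with calendar months. With one delay the result is at most 28 + 14 = 42 or 31 + 14 = 45 days old, inside 56.

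**The case against.** **Other controls exist.** Sections 2.1.1.8, 2.1.1.9 and 2.4 B put history, physical examination, blood count and liver tests within 16 days of treatment, and section 11.2.6 forbids vaccinia in immunodeficient men. These are real safeguards, and a reader might infer from the ages above that Arm B men reach vaccinia unchecked, which is not so. Still, an infected man can pass: AST and ALT up to 2.5 times the upper limit and granulocytes from 1000/mm³ are accepted, no CD4 limit is set, phenotyping is not required at every site (Appendix D; footnote 12), and the prohibition works only for a known condition. Repeats if clinically indicated do not schedule a test for an infection without symptoms.

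**Enrolment may not mean M-6.** The arm-specific definition stands in 2.2 C, not 2.2 B, and section 2.1.2.7 equates enrolment with a Day 1 visit. The competing usage is there, but 2.2 C is the only place that defines the term by arm. The serology mark also sits under screening, and section 2.3.2 assigns the arm only after the eligibility checklist is sent.

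**Comparisons that a reader might draw.** The Arm B scans share the 8-week window ("Screening Tc99 scintigraphy and CT-CAP or MRI will be obtained within 8 weeks prior to enrollment") and carry a later mark, which could suggest that the plan refreshes dated eligibility items before dosing. It does not show that: section 3.5.4 and footnote 6 make the later scans routine six-monthly restaging, which can be deferred. The exclusion for "corticosteroids deemed systemic by investigator within 28 days before the first planned dose of PROSTVAC" is a drug washout, dated to the dose by its nature, and is no precedent for repeating a laboratory test.

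**The risk is small.** Harm needs a new infection, no clinical sign, passing laboratory values, sufficient immune impairment and then a complication. The documents give no rate for that sequence. This limits the weight of the point but does not close the gap.

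**Conclusion.** The point holds. If the plan is followed as written, an Arm B man receives replication-competent vaccinia on serology that is 168 to 224 days old (28-day months) or 181 to 240 days old (calendar months). One permitted delay takes the maximum to 238 or 254 days. The Arm A maximum is 56 days.

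This rests on carrying the 2.2 C meaning of enrolment over to 2.2 B and footnote 3, and on an assumed length for a surveillance month. Neither month convention changes the conclusion.

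Three stronger readings are not supported:

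- The ratio of ages is not a ratio of risks. The absolute risk is unquantified and probably low, and nothing here counts harmed men.
- The infectious-vaccine rationale is stated for HIV. The hepatitis part rests on possible immune impairment alone.
- Delays might be thought to accumulate over the six visits from M-5 to C1D1, adding 6 × 14 = 84 days and giving 308 or 324. The text does not say that they do, so only one delay is counted.

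The ECG dates are a separate contradiction. Section 2.4 A already carries the right safety intent, so this is a documentation error and adds nothing to the serology argument.

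The change is worth making because the possible consequence is severe and the remedy is small.

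**What to change.** 1. Leave the 2.2 B entry test as it is, since the arm is not known when eligibility is confirmed.
2. Add to section 2.4, the Arm B calendar and Arm B footnote 3 a repeat HIV, HBV and HCV test within 8 weeks before C1D1, with results available before vaccinia is released. It can be drawn at M-1, where a PSA draw appears to be scheduled (the calendar columns are hard to read in the extracted text). It can instead go with the 2.4 B bloods in the last 16 days, if the result returns in time.
3. Change Arm B footnote 5 so that the ECG falls within 8 weeks before treatment initiation, matching 2.4 A.

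**Cost.** A small extra blood volume and the assays, for 36 planned evaluable Arm B men, or at most about 110/2 = 55 if the whole accrual ceiling were randomised. Appendix D lists one 8 mL tube for HIV and none for hepatitis, so the full volume is not documented. The ECG change adds nothing beyond what 2.4 A already requires. A vaccination may occasionally be deferred or withheld, which would slightly reduce the numbers for the Arm B secondary analysis of growth rate at 12 against 6 months.

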- have other acute, chronic, or exfoliative skin conditions (e.g., burns, impetigo, varicella zoster, severe acne, contact dermatitis, psoriasis, herpes or other open rashes or wounds), until the condition resolves.

- are pregnant or intend to become pregnant (due to the potential risk of fetal vaccinia); or are breast-feeding (due to the potential risk of contact transmission and inadvertent inoculation). It is currently unknown if vaccinia virus or antibodies are excreted in breast milk. Patients (*i.e.*, vaccinees) should avoid fathering a child for at least 4 months following completion of therapy with the recombinant vaccine.
- are in close contact with children less than 3 years of age (due to the potential risk of contact transmission and inadvertent inoculation).
- are immunodeficient or immunocompromised (by disease or therapy), including individuals with HIV infection.

Additionally, do not administer the recombinant vaccinia vaccine if the vaccinee:

- has a moderate or severe acute illness, until the illness resolves.
- is undergoing topical steroid therapy for inflammatory eye diseases, or undergoing therapy with systemic steroids; potential immune suppression increases risk for vaccinia-related complications.
- At this time, until a more definitive causal relationship is determined, it is recommended that patients with known CHF or clinically significant cardiomyopathy, not be vaccinated with recombinant vaccinia-based vaccines, due to the potential for development of myocarditis and/or pericarditis.

Although the CDC believes that there is no evidence to conclude that the licensed vaccinia vaccine used in the Smallpox Vaccination Program causes angina or heart attacks, it acknowledges a possible causal relationship between the vaccination and heart inflammation. The CDC continues to study the relationship, but in the meantime, recommends excluding individuals with underlying heart disease from participation in the current Smallpox Vaccination Program. Patients are being immunized with recombinant vaccinia vaccines with therapeutic intent and will be evaluated for cardiovascular risk factors and recent or symptomatic cardiac events per protocol eligibility criteria. Patients will be encouraged to minimize cardiovascular disease risks and encouraged to follow risk reduction according to standard medical practice.

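### The Arm B calendar dates its only ECG from enrolment (M-6), so a site following it gives the first vaccinia dose on a tracing about 24 to 34 weeks old, against the 8-week limit in 2.4 A

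*Combined protocol and SAP*

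**What the plan says.** Section 2.4 Baseline Evaluation, item A, asks for "Baseline electrocardiogram (EKG) on all patients, and appropriate cardiologic evaluation, as clinically indicated, to provide baseline function" and to pick out men who need close watching because of vaccinia's cardiac risks. Its time limit is 8 weeks "prior to treatment initiation".

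In Appendix C, the Surveillance Arm calendar carries a single ECG mark, under Screening/Baseline, with none at any later visit. Footnote 5 to that mark says "Baseline ECG will be obtained within 8 weeks prior to enrollment". Footnote 11, on the column heading, refers the reader to 2.2 and 2.4.

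Section 2.2 Screening Evaluation, item C, defines the reference point by arm: "prior to enrollment (cycle 1 day 1 for immediate treatment arm [Arm A], or M-6 visit for surveillance first arm [Arm B". Section 2.2 itself lists no ECG. In Arm B the vaccinia dose follows six months of surveillance.

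The Immediate Vaccine Arm calendar repeats footnote 5 word for word.

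**The concern.** With the one ECG that the Arm B calendar schedules, a site cannot meet both footnote 5 and 2.4 A. The two dates coincide in Arm A, where enrolment is the day of the first dose. In Arm B they are six months apart. Coordinators commonly work from the calendar, and there the ECG-specific footnote gives the enrolment date.

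Two things would be lost:

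- **The safety check.** The ECG is the only cardiac test scheduled for every man before vaccinia. A tracing more than five months old cannot show a silent change since enrolment. It is also a weaker comparator if myopericarditis is suspected after the dose. Section 11.2.6 reports an identifiable abnormality in 46 of 61 reviewed ECGs (75.4%) among military myopericarditis cases.
- **Compliance.** Section 7.1.8 counts any departure from the protocol as a deviation, and 7.2.1 requires all deviations to be reported within 7 days. Each Arm B man dosed on the footnote 5 tracing alone is one such departure, for up to about 36 men at the planned evaluable number.

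The 0-to-6-month growth-rate comparison in section 8 does not depend on the ECG.

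**Working it through.** This is date arithmetic; no power or error-rate calculation is involved.

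**Inputs**

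- Limit in 2.4 A: 8 weeks = 56 days before treatment initiation.
- Window in footnote 5: 0 to 56 days before enrolment.
- Enrolment (2.2 C): C1D1 in Arm A, the M-6 visit in Arm B.
- M-6 to first vaccinia dose in Arm B: 6 months (Appendix C). The calendar header says "1 cycle = 28 days; C=Cycle; D=Day", which is stated for treatment cycles. Whether surveillance months are also 28 days is not stated, so both readings are shown.
- Permitted slippage (Appendix C): "All patient visits can be delayed by 2 weeks for logistical issues", with exceptions only for weeks 3 and 5.

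**Formula**

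ECG age at first vaccinia dose = (days from ECG to enrolment, 0 to 56) + (days from enrolment to first dose).

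**Arm A.** Enrolment to first dose = 0 days, so the age is 0 to 56 days. Footnote 5 reproduces the 8-week limit.

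**Arm B**

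| Reading of six months | Enrolment to dose | Youngest ECG | Oldest ECG | Excess over 56 days |
|---|---|---|---|---|
| 28-day months | 6 × 28 = 168 days | 168 days = 24.0 weeks | 168 + 56 = 224 days = 32.0 weeks | 112 to 168 days (16 to 24 weeks) |
| Calendar months | 6 × 30.44 = 183 days | 183 days = 26.1 weeks | 183 + 56 = 239 days = 34.1 weeks | 127 to 183 days (18.1 to 26.1 weeks) |

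A full two-week visit delay raises the oldest value to 224 + 14 = 238 days (34 weeks) or 239 + 14 = 253 days (36.1 weeks).

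The 8-week limit is not reproduced in Arm B on either reading. The headline span of 24 to 34 weeks takes its lower end from 28-day months and its upper end from calendar months.

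**Scale of the clinical risk.** Section 11.2.6 reports 67 symptomatic myopericarditis cases among 540,824 military vaccinees and 21 myo/pericarditis cases among 37,901 health care workers. If those smallpox-vaccine rates applied to 36 men, the expected number would be 36 × 67/540,824 = 0.004 to 36 × 21/37,901 = 0.02. Those populations and the route of vaccination differ from this trial, so this indicates only the order of magnitude.

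**The case against.** The strongest reply is that the requirement is already in the body text for all patients, and that footnote 11 sends the reader of that column to 2.4. On this view an appendix footnote is loosely worded and no assessment is missing. It is true that a site following 2.4 A complies, so the ECG ages above are conditional on following footnote 5. But footnote 11 is a general pointer, whereas footnote 5 is specific to the ECG and gives a different date. The pointer reveals the conflict without settling it.

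Other arguments:

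- **Enrolment might mean the first vaccination day.** The surgery exclusion in 2.1.2.7 equates enrolment with the Day 1 visit, without separating the arms. Section 2.2 C does separate them and names M-6 for Arm B. Nor can treatment initiation mean the start of surveillance, since 2.4 A ties the ECG to vaccinia.
- **The calendar may intend one study-entry baseline.** ECOG status, urinalysis and CK/uric acid/total protein are also 2.4 items marked only at Screening/Baseline in Arm B. This observation stands, and those items deserve the same check. It does not excuse the ECG, whose stated purpose is tied to vaccinia. The no-repeat allowance belongs to 2.4 B, not 2.4 A, and even there holds only "prior to start of treatment (these tests will not need to be repeated if they were done at screening within the appropriate timeframe".
- **The later CBC and chemistry marks prove little.** Those tests are routine monitoring each cycle, so their reappearance does not show that an ECG was forgotten. This is fair, and the finding does not need that contrast.
- **The consequence is small.** No eligibility criterion in 2.1 or dosing rule in 3.3 uses an ECG result. History and examination are due within 16 days of treatment, visits during surveillance also record history and adverse events, and 11.2.6 separately says "it is recommended that patients with known CHF or clinically significant cardiomyopathy, not be vaccinated with recombinant vaccinia-based vaccines". This stands and limits the severity.

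**Conclusion.** The concern holds. Footnote 5 of the Arm B calendar conflicts with 2.4 A. Followed as written, it yields an ECG 24 to 32 weeks old (28-day months) or 26 to 34 weeks old (calendar months) at the first vaccinia dose, against a limit of 8. The smallest excess on any reading is 16 weeks.

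The conclusion rests on Arm B enrolment being the M-6 visit, as 2.2 C says, and on a site relying on the calendar for timing. The length of a surveillance month affects the size of the gap but not its existence.

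This is an inconsistency that should be corrected. Its safety consequence is limited mainly to a silent ECG change between enrolment and dosing, and it has no effect on the primary analysis.

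**What to change.** In the Arm B calendar, reword footnote 5 to 'within 8 weeks prior to treatment initiation' and add an ECG mark in the 8 weeks before C1D1. Arm A needs no change in practice; the same wording could be used there for consistency. The single-mark 2.4 B items noted above can be checked in the same amendment.

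The cost is one footnote and one calendar mark, plus one ECG per Arm B man before vaccinia (about 36), which 2.4 A already requires. Whether the total number of tracings rises depends on the entry ECG. Randomisation sits in the same Screening/Baseline column, so if the ECG is done before the arm is known, Arm B men will have a second one. If it is done only after assignment, the Arm B tracing can be taken once, before C1D1. The drawback is that a cardiac finding would then first emerge months after randomisation. Keeping the entry ECG and repeating it before C1D1 avoids that, at one extra tracing per Arm B man.
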